The blinding of the participants to group assignment was not possible, since participants knew which diet they were following. The blinding of the researchers to the subjects' identity was achieved by the coding of all study materials (urine containers, questionnaires, and diaries). The study personnel who obtained the outcome measurements were also not informed of the group assignment. The personnel who delivered the intervention did not take any outcome measurements. All outcome assessors and data analysts were kept masked to the allocation.

11b	If relevant, description of the similarity of interventions	
11c		If blinding was not possible, description of any attempts to limit bias
	Not relevant.	Not relevant.

Statistical methods†	12	Statistical methods used to compare groups for primary outcome(s); methods for additional analyses, such as subgroup analyses and adjusted analyses	When applicable, details of whether and how the clustering by care providers or centers was addressed How clustering was taken into account
----------------------	----	--	--

During the design phase of the study, power calculations were conducted to estimate the optimal sample size of a study assuming 80% power with a two-sided 5% significance level to detect a minimal detectable difference of 0.1 units in OSI biomarkers between the organic and conventional treatment, while the within subject standard deviation of the biomarker of effect was assumed to be 0.5. The clustering was not addressed, but the within cluster within period and the within cluster between period intra cluster correlation estimates were assumed equal.

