was not requested to include it in the dairy. Moreover, the diary was used to note any sickness and any pesticide use at home. The frequent telephone communication with parents, the weekly visits at schools, and the daily communication with the restaurant were key factors that further enhanced the compliance to the organic diet treatment. In order to encourage adherence to the organic diet until the end of the period, a public event was organized during the mid-period of the study with activities for the participating children and free sampling of organic food products.

Flow of schools and children

The flow of schools and children through the trial is reported in accordance with the CONSORT extension statement for cluster trials.⁵ The flow diagram includes the number of eligible and recruited schools, number of eligible and recruited children and then, by allocated group, the number of children who completed the trial, the number lost to follow-up and the numbers included in the analysis.

Withdrawals

Parents could choose to withdraw their children from the study at any point of the organic diet intervention without having to provide any explanation. Children who discontinued completing the data collection prior to the end of the trial period were withdrawn but their already collected data remained available for analysis, unless parents had requested otherwise. Reasons for withdrawal were documented wherever possible.

Outcomes

Per the trial protocol, the primary outcomes are the biomarkers of exposure to pesticides using two non-specific pesticides metabolites (3-phenoxybenzoic acid (3-PBA), 6-chloronicotinic acid (6-CN)) measured in first morning urine voids collected any two up to six time points. The secondary outcomes are the biomarkers of oxidative stress/inflammation (8-iso-prostaglandin F2a (8-iso-PGF2a), malondialdehyde (MDA) and 8-hydroxy-2'-deoxyguanosine (8-OHdG)) measured in the same urine samples.

Sample size

To estimate the sample size, the PS software for calculating sample size was used.⁶ We used the paired t test study design for calculating the power of this test, assuming that each subject has a pair of values (one for conventional and one for organic diet). The

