variable used for the estimation of the sample size was a biomarker of inflammation (C-reactive protein), because the biomarkers of inflammation/oxidative stress were one the primary outcomes for the trial and we information on pesticide levels were unavailable at that time. The lack of pertinent human studies with similar setting and characteristics to the present study that involved exactly the same biomarkers of effect (8-OHdG and isoprostanes) led us to use the available human study of CRP.⁷

The input parameters were: significance level, within patient standard deviation or standard deviation of the difference between the two values for the same patient, power and minimal detectable difference in means. Based on the literature, the within subject standard deviation of CRP was assumed to be 0.5,⁷ and we hypothesized a minimal detectable difference in biomarkers of effect (CRP) between the organic and conventional treatment to be 0.1, based on other intervention studies.⁸⁻¹⁰ Assuming a power of 80% and a two-sided 5% significance level, the sample size for this two-treatment crossover study was estimated to be 200 children. The clustering was not addressed, but the within cluster within period and the within cluster between period intra cluster correlation estimates were assumed equal.

Statistical analysis

General principles

Participant population

The analysis population consists of all children excluding withdrawn children whose parents also withdrew their consent for the data to be used or children who left the trial with less than 12 days in the organic diet arm and did not provide any samples during the organic diet intervention.

Whilst it was not anticipated that there would be children who cross-over their trial group (i.e. change from intervention to control, or vice versa), any two exceptions were documented. Two children (following their parents' signed consent) decided to enroll in the study after the study was initiated and at the end of the conventional arm, right before the beginning of the organic diet treatment, based on their school's group (Group 2). These children provided a baseline sample, 2 or 3 samples during the organic period and 2 conventional samples after the organic diet period ended, so they basically followed the opposite design based on their school. However, they did follow the

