organic period at the same time as their classmates. These two children were allocated to Group 1 for analysis purposes. There was no issue of transferring knowledge within the school about the organic diet intervention from these two children since they were participating in the intervention arm at the same time the rest children of the school were. The only difference was that these two children participated in the conventional arm after the end of the organic diet and not before the beginning of the organic diet treatment, as the rest of the children of their respective school.

The full analysis population consists of all children who followed the organic treatment for at least 12 days and provided at least one urine sample during the organic diet intervention.

Levels of confidence and p values

Statistical tests and confidence intervals were two-sided. 95% confidence intervals will be presented wherever possible. The statistical significance level set will be at the 5% level.

Unadjusted and adjusted analyses

All outcomes were used with for creatinine levels to account for urine dilution. If outcomes are not normally-distributed and the analyses require the normality assumption, then outcomes will be log-transformed (natural logarithm).

Multiple testing

Multiple testing will be accounted for, using the Benjamini-Hochberg (false discovery rate, FDR) method considering all the regression parameters of the primary and post-hoc analyses. Q-value <0.05 indicates statistical significance of an association after controlling the false discovery rate at 5%.

Handling of missing data and data below LOD

Missing values in the questionnaire were not imputed. For the biomarkers data below the limit of detection (LOD), imputation was performed based on existing suggestions for handling non-detect urinary measured concentrations data.¹¹ For outcomes that contained $<20\%$ values below the detection limit, values $<\text{LOD}$ were imputed as $\text{LOD}/2$ and for outcomes that contained $\geq 20\%$ values below detection, values $<\text{LOD}$ were imputed with regression on order statistics (ROS). With the ROS method, non-detect data are replaced based on a probability plot of detects. Outcomes with $>70\%$

values below detection, were used as binary variables in the primary, post-hoc and sensitivity analyses.

Baseline characteristics

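### The 80% power with 200 children is for one unadjusted 5% test on a CRP proxy, while the SAP judges regression effects by q<0.05, where power is at most that figure and depends on an uncounted family

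*SAP*

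**What the plan says.** **Power.** The SAP's Sample size section states: "Assuming a power of 80% and a two-sided 5% significance level, the sample size for this two-treatment crossover study was estimated to be 200 children". Behind it is a single paired comparison ("We used the paired t test study design for calculating the power of this test"). The variable is CRP, with a difference of 0.1, and "the within subject standard deviation of CRP was assumed to be 0.5". Protocol item 7 gives the same calculation. Protocol item 12 repeats it for the oxidative stress/inflammation (OSI) markers: "assuming 80% power with a two-sided 5% significance level to detect a minimal detectable difference of 0.1 units in OSI biomarkers". None of these places has a multiplicity term.

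**General level.** Under Levels of confidence and p values, the SAP says: "The statistical significance level set will be at the 5% level". It also promises 95% intervals wherever possible.

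**Multiplicity.** The next-but-one SAP section, Multiple testing, applies Benjamini-Hochberg to every regression coefficient in the primary and post-hoc analyses and concludes: "Q-value <0.05 indicates statistical significance of an association after controlling the false discovery rate at 5" percent. It neither lists nor counts the coefficients. It does not say how this rule relates to the general level.

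**Protocol.** The statistical methods under item 12 do not mention false discovery rate control.

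**The concern.** Power is the probability that the planned decision rule declares the targeted effect. The 80% was computed for a rule that compares one p-value with 0.05. For the diet effects in the mixed and logistic models, the SAP calls an effect significant when its q-value is below 0.05. Under Benjamini-Hochberg, the p-value threshold for any one coefficient lies between 0.05/m and 0.05, where m is the number of tests in the family. The stated power is therefore an upper bound for the SAP's rule.

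Two things are at stake. A reader may take 80% as the chance that the SAP's analysis detects the planned difference, and so misjudge a null result. Also, a diet effect with p<0.05 but q≥0.05 has no explicitly assigned verdict, because the SAP does not say that the multiplicity rule takes precedence over its general level.

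**Working it through.** **Inputs.** From the SAP's Sample size section: difference 0.1, SD 0.5, power 80%, two-sided 5%, n=200, one pair of values per child. Standardised difference: 0.1/0.5 = 0.2. The family size m is not in the documents and is assumed below.

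**Step 1: reproduce the plan's figure.** Normal approximation: n = [SD × (z0.975 + z0.80)/difference]² = [0.5 × (1.960 + 0.842)/0.1]² ≈ 196.2, rounded up to 197. The exact non-central t calculation gives n=199, and 80.4% power at n=200. The stated 200 is right for one unadjusted two-sided 5% test, with 0.5 used as the SD of the paired difference. A one-sided 5% test would need 155. Taking 0.5 as the SD of each single measurement (SD of the difference 0.5√2) would need 395.

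**Step 2: power at the lowest Benjamini-Hochberg threshold.** Same non-central t calculation at n=200, with level 0.05/m:

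| m | 0.05/m | Power at n=200 | n for 80% |
|---|---|---|---|
| 1 | 0.05 | 80.4% | 199 |
| 2 | 0.025 | 71.5% | 241 |
| 5 | 0.01 | 59.1% | 296 |
| 15 | 0.0033 | 44.5% | 361 |
| 20 | 0.0025 | 41.0% | 379 |
| 60 | 0.00083 | 29.0% | 444 |

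The last column only shows which level the 200 belongs to. It is not a proposal to enrol more children.

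**Step 3: size of the family.** The primary model has treatment, time and the baseline value, plus a treatment-by-time interaction if kept. Over the five listed biomarkers that is 5 × 3 = 15 or 5 × 4 = 20 coefficients, intercepts excluded. The post-hoc models add more; 60 in all is an assumption. Families of 2 (primary outcomes) or 5 (primary plus secondary) would hold only if the family were restricted to the diet effects, which the SAP does not do.

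**Step 4: power under the full Benjamini-Hochberg procedure.** Simulation with independent tests and a normal approximation. Each real diet effect has mean 0.2 × √200 = 2.83 on the z scale; strongly non-null coefficients have mean 8. The same approximation gives about 81% for p<0.05 alone.

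| Assumed family | Power for a real diet effect, q<0.05 |
|---|---|
| m=2, one real | 72% |
| m=5, one real | 60% |
| m=2 / m=5, all real | 79% / 78% |
| m=15 / m=20, one real, rest null | 47% / 43% |
| m=15 / m=20, one real, five baseline coefficients strongly non-null | 70% / 66% |
| m=60, one real, rest null | 31% |

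**Step 5: results on which the rules differ.** Every q<0.05 result also has p<0.05, so the disputed share is the single-test power minus the power in Step 4. For a real diet effect it is about 20% at m=5 with one real effect, 3% at m=5 with all five real, and 50% at m=60 with one real effect. With five strong baseline coefficients and one real diet effect, it is 81 − 70 = 11 points at m=15 and 81 − 66 = 15 points at m=20.

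**The case against.** A reader might infer four stronger things, none of which the documents support.

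- **That 200 is miscalculated.** It is not. It reproduces, and the SAP openly conditions it: "Assuming a power of 80% and a two-sided 5% significance level". It never claims to be power under the q rule.
- **That the protocol sets a rival decision rule.** The 5% in Protocol items 7 and 12 is an input to the power calculation. The only other threshold in the protocol's statistical methods is p=0.05 for dropping the interaction. The protocol is silent on the decision rule, and multiplicity detail that appears only in a SAP is not a contradiction.
- **That the SAP contradicts itself.** The general 5% level can be read as a default that the more specific Multiple testing section overrides for regression coefficients. The default still covers the baseline comparisons, the one-sample t-test of percent change and the Wilcoxon comparison of periods. This reading is sensible, but the SAP does not state it. What remains is a missing order of precedence.
- **That power under q<0.05 is about 60% to 79%.** That range needs a family of 2 to 5 diet effects, which is not the SAP's family. Larger families can give far less. Strong nuisance coefficients can restore much of the loss.

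It is also fair to object that recalibrating the level does not give the power of the planned models. CRP is not a listed outcome, no effect size is given for 3-PBA or 6-CN, 6-CN goes to a logistic model, and clustering was not addressed. This stands, and it limits what any restated figure can claim. The trial is also reported as already conducted, so a restated power alters no estimate. It does alter how a non-significant result is read.

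**Conclusion.** The point holds as a mismatch between the power statement and the decision rule. The 80% belongs to one unadjusted two-sided 5% paired t-test on CRP. Under the SAP's q<0.05 rule, power for the same effect is at most that.

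The direction is certain because q is never below p. The size is not, because the family is uncounted and the number of non-null coefficients is unknown. The assumed scenarios run from 78–79% (a family of 2 to 5 diet effects, all real) to about 31% (60 coefficients, one real). The 15 to 20 coefficients of the primary models give 43–47% or 66–70% with one real diet effect, depending on whether the other coefficients are null or five baseline terms are strong. All these figures assume independent tests, n=200 and the plan's standardised difference of 0.2. They illustrate the effect of the rule and are not the power for 3-PBA or 6-CN.

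**What to change.** 1. **Power statements (Protocol items 7 and 12; SAP Sample size).** Describe the 80% as power for a single unadjusted two-sided 5% test on the CRP proxy, and say that it is lower under q<0.05. Give any power figure under false discovery rate control only with its family and assumptions, not as one fixed range.
2. **SAP, Levels of confidence and Multiple testing.** State that q<0.05 decides the diet effects in the regression models, that the 5% level applies to tests outside that family, and that raw p-values and 95% intervals are unadjusted. List and count the coefficients in the family.
3. **Protocol item 12.** Add the q rule.

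The cost is wording in two documents. No added enrolment is proposed. The downside is that the stated power becomes less favourable.

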Descriptive statistics were used to summarize the demographic and other characteristics of participating children. Categorical variables were described with frequencies and percentages, normally-distributed continuous variables as mean $\pm$ SD and non-normal continuous variables as median and interquartile range (25th-75th percentiles). Box plots were used to visually inspect the biomarker data. For data below LOD, imputation was performed based on existing suggestions for handling non-detect data. For 6-CN and 3-PBA, the percentage of data below LOD was 72% and 23% accordingly, so the imputation was performed using the regression on order statistics (ROS). For MDA and creatinine, the percentage of data below LOD was very low ( $\approx$  1%), so the LOD/2 imputation was used. The baseline characteristics were compared between the study groups with t-test for the normal continuous variables or Wilcoxon test, and chi-square for the normal, non-normal, and for the categorical variables, respectively.

The percent change between the baseline (last sample of conventional treatment before the start of the organic treatment) and after 40 days of organic diet (last sample of organic treatment) was determined with one sample t-test for all biomarkers (log-transformed) and the change between the conventional and organic treatment (medians) was determined using Wilcoxon test for all biomarkers (non-normal variables).

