The change in outcomes (biomarkers of pesticide exposure and of oxidative stress) between the baseline and the end of the organic period was assessed with the percent change between the last sample of the conventional treatment period (before the start of the organic treatment) and the last urine sample of the organic treatment period. The percent change was estimated only for the participants who completed the full course of the organic treatment. A one-sample T-test was used to assess whether the percent change was significantly different than zero.

Overall change between conventional and organic period

The overall change in outcomes between the conventional and organic period was assessed using the overall difference in median levels. The conventional period consists of all conventional samples, including the baseline sample, and the organic period will consist of all organic samples for all participants, regardless of the duration for which they followed the organic treatment. The overall difference in the median levels of the outcomes between the conventional and the organic period was assessed using the unpaired T-test if the outcomes were normally distributed or using the non-parametric Wilcoxon test if the outcomes were non-normally distributed.

Primary analysis of outcomes

Linear mixed-effect regression models were used for continuous outcomes and logistic models for binary variables (i.e. those with >70% values below LOD), to account for the duration and the effect of treatment. To account for the clustering of participants within schools and the repeated measures within person, the models will include student-level and school-level random intercepts with unsupervised covariance matrix. Fixed effects were: the treatment condition (organic or conventional) and time (days of treatment, where time=0 was the start of the treatment). An interaction term for the treatment condition and time were considered and dropped when not meeting the threshold of p-value=0.05. The models were adjusted for the baseline value of the outcome in order to account for the background biomarker levels of the participant. The baseline sample was a conventional sample for both groups but it was not consecutive to the conventional phase due to the study design and, thus, it is indicative of each participants exposure prior to participation in the study

In all regression models, the continuous variables, other than time, were centred at the population means.

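### The 23% of 3-PBA values below the LOD enter the primary mixed model as ROS fill-ins, with no rule tying them to diet, child or sample and no check; pooled fitting would mildly attenuate the diet effect

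*SAP*

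**What the plan says.** The Protocol (Item 12, Statistical methods) reports the non-detect shares: "For 6-CN and 3-PBA, the percentage of data below LOD was 72% and 23% accordingly". The SAP (Handling of missing data and data below LOD) uses LOD/2 below 20% non-detects and ROS from 20% upward. Its only account of ROS is that "With the ROS method, non-detect data are replaced based on a probability plot of detects". Outcomes with more than 70% of "values below detection, were used as binary variables in the primary, post-hoc and sensitivity analyses".

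SAP, Primary analysis of outcomes: "Linear mixed-effect regression models were used for continuous outcomes and logistic models for binary variables". The linear model has diet and time as fixed effects and random intercepts for student and school. On the baseline covariate: "The models were adjusted for the baseline value of the outcome in order to account for the background biomarker levels of the participant".

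The two planned sensitivity analyses (SAP, Sensitivity analysis) drop the baseline adjustment and drop two children who followed the opposite order. Neither varies the handling of non-detects.

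**The concern.** ROS estimates the lower tail of a distribution. It yields a set of plausible values for the non-detects as a group, which is enough for a median, a quartile or an SD. It does not say which value belongs to which child, visit or diet. A within-child comparison of diets needs exactly that link.

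Two things can follow. If one plot serves both diets, non-detects get the same average fill under either diet, so the part of the diet effect that lies below the LOD is lost. And if there is a single LOD, all non-detects are tied and something arbitrary, such as row order, must decide which sample gets which fill. At stake are one of the two primary effect estimates and its confidence interval. Baseline non-detects are filled in the same way before they serve as a covariate.

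**Working it through.** **1. Which rule applies.** 3-PBA: 23% is at least 20%, so ROS; 23% is not above 70%, so it stays continuous. 6-CN: 72% is above 70%, so it is binary in the models and ROS fills do not enter there. The documents give no figure for the effect of ROS on the diet estimate, so there is none to reproduce. The planned 200 children are used below only as the simulation size.

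**2. What ROS supplies.** With one LOD and m non-detects, fill j is a + b·z(0.23·j/(m+1)), where a and b come from regressing ln detects on normal quantiles. Diet, child and visit do not appear. With 200 children and 6 samples (SAP, Intervention), m = 0.23 × 1,200 = 276. The fills run from z(0.23/277) = -3.15 to z(0.23 × 276/277) = -0.74. At an assumed SD of 1.0 ln unit that is 2.40 units, an 11-fold range (e^2.40), so the assignment matters.

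**3. Attenuation by hand.** Assume ln 3-PBA normal with SD 1.0, equal numbers of conventional (baseline included) and organic samples, true GMR 0.70 (ln = -0.357), and the LOD at the pooled 23% point.
- Non-detects: 17.6% conventional, 28.4% organic.
- True mean of non-detects, relative to the conventional mean: -1.469 conventional, -1.551 organic.
- Pooled mean: (0.176 × -1.469 + 0.284 × -1.551)/0.460 = -1.519, given on average to both diets.
- Shift in the conventional mean: 0.176 × (-1.519 + 1.469) = -0.009. Shift in the organic mean: 0.284 × (-1.519 + 1.551) = +0.009.
- Loss: 0.018 of 0.357, or 5%. Estimated GMR: exp(-0.357 + 0.018) = 0.71.

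**4. Simulation with diet, time and baseline in the model.** 200 children, 6 samples, sequence ratio 1:2.5 (Protocol, Item 3a), random child intercept, 200 runs per setting. Assumed: total ln SD 1.0, within-child correlation 0.3, one LOD, no school effect; no creatinine variation in this table.

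| Handling of non-detects | True 0.70 | True 0.50 |
|---|---|---|
| No censoring | 0.701 | 0.503 |
| ROS fills in true rank order | 0.701 | 0.503 |
| Pooled ROS, random order | 0.714 | 0.516 |
| Pooled ROS, child then visit | 0.715 | 0.517 |
| Pooled ROS, visit then child | 0.759 | 0.552 |
| Pooled ROS, conventional rows first | 0.851 | 0.613 |
| Pooled ROS, organic rows first | 0.615 | 0.455 |
| ROS fitted within each diet | 0.700 | 0.501 |
| Left-censored mixed model (40 runs) | 0.699 | 0.494 |

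The true-rank row shows that the fills as a set are sound; the assignment does the harm. In random order the log effect is 1 - 0.337/0.355 = 5% smaller (true 0.70) and 1 - 0.661/0.688 = 4% smaller (true 0.50). Re-shuffling the rows of one fixed dataset (true 0.70) moved the GMR over about 0.669-0.714, an SD of 0.014 log units against a model SE of 0.054.

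**5. Coverage, from a within-child contrast.** Assumed: between-child SD 0.5, within-child 0.7, dilution SD 0.5, 2 conventional and 3 organic samples, true GMR 0.70.
- Random or child-sorted allocation: GMR 0.711-0.713, coverage 92-94%. The hand figure agrees: a bias of 0.018/0.054 = one third of an SE implies coverage of 93.7%.
- ROS after creatinine correction, with sample-specific limits: GMR 0.722-0.725, coverage 87%. The log effect is 1 - 0.326/0.357 = 9% to 1 - 0.322/0.357 = 10% smaller. Row order no longer matters.
- Ties filled in date order, ROS before creatinine correction: GMR 0.75-0.77, coverage 51-68%; with no true effect, 24-42% false positives. Reverse date order: GMR 0.665, coverage 82%.

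**The case against.** The strongest reply is that most of this fills silences. The SAP does not say that ROS was pooled over diets, that there was one LOD, that ties were filled by row, or that ROS came before the creatinine step. ROS fitted within each diet shows almost no attenuation. ROS on creatinine-corrected values removes the dependence on sorting, and with no true effect it gave a GMR of 1.005 with coverage 93%. With random or child-sorted rows the bias is about a third of a standard error. The coverage figures come from a simpler model than the SAP's, without school intercept, time or baseline. The documents are written after data collection, so replacing the primary model now would be a data-aware change.

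All of that stands, and it limits the point. A reader might infer that the plan does attenuate the 3-PBA effect, or that the result hangs on how the file was sorted and carries a false-positive rate of 24-42%. The documents support neither. Attenuation depends on pooled fitting and reverses under some row orders; the sorting figures need several unstated conditions together.

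The reply does not remove the defect. The SAP describes neither fitting within diet nor an assignment rule. Attenuation remains when pooled ROS follows creatinine correction, and is larger there. No planned analysis would reveal any of it.

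**Conclusion.** The point holds as a weakness in the primary 3-PBA analysis. A method suited to summaries feeds a child-level regression, the step that determines its bias is unspecified, and nothing checks it.

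If ROS is pooled, the likely size is mild: about 4-5% off the log effect when allocation is unrelated to diet, and about 9-10% if ROS follows creatinine correction (true GMR 0.70 in both). Large bias in either direction is a conditional scenario. These sizes rest on assumed SDs, within-child correlation and GMRs, which the documents do not give for 3-PBA. The models for 6-CN are not affected. Nothing here shows that the reported 3-PBA result is wrong.

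**What to change.** For 3-PBA, and any outcome with 20-70% of values below the LOD, estimate the diet effect in one of two ways:

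- a left-censored (Tobit) mixed model with the SAP's fixed and random effects, censored at the LOD, or at sample-specific limits if values are creatinine-corrected; or
- multiple imputation below the LOD, conditional on diet, time and child.

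State also how a baseline value below the LOD enters as a covariate. Imputation can settle this in the same step; a censored likelihood for the outcome does not. Keep ROS for descriptive medians and quartiles. How dilution is adjusted for is a separate choice and need not change.

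If the primary model is not to be changed after data have been seen, report the censored model beside it as a sensitivity analysis. State whether ROS was fitted pooled or by diet, before or after creatinine correction, with how many LODs, and how fills were assigned to samples.

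Cost: one SAP paragraph, slightly more programming and a convergence check; no new data. The check matters because there are only six schools, and the censored model was tried here with a child intercept only, in 40 runs per setting (Monte Carlo error about 0.064/√40 = 0.01 log units at a true GMR of 0.70), without an assessment of coverage.
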